The pharmacists will review the home BP values with the intervention subjects. If the home BP values are controlled, the pharmacist will continue to monitor home BP values.

However, if the pharmacist identifies issues such as poor medication adherence, inability to afford medications or other issues, they will work with the patient and physician to optimize therapy and/or reduce cost. If the pharmacist suspects white coat hypertension, they will make a recommendation to the physician to refer the patient to the University of Iowa ambulatory blood pressure service.

If BP values are elevated, the pharmacist will assess medication adherence, ability to pay for medications and whether the regimen is optimal to control BP based on patient demographics and co-existing conditions. The pharmacist will communicate recommendations for lifestyle and other changes directly to the subject. If medication changes are needed, the pharmacist will communicate to the physician through the electronic medical record. The pharmacist may recommend:

1. Increased dose of a medication.
2. Addition of a medication.
3. Discontinuation of a medication.
4. Modification of the regimen to optimize therapy, improve convenience (e.g. fixed-dose combinations) or reduce cost.

All participants in the pharmacist intervention group will continue to have access to a research pharmacist for the entire 12 months of follow up. Additionally, they will be asked to continue measuring and texting BP values (1 morning, 1 evening) for 3 days each month throughout the 12-month follow up.

The pharmacists will typically contact with the participants every 2 weeks while BP is not controlled. Once BP is controlled, they will continue monitoring the participant's records and home BPs and make contact at least every 2 months to support adherence and reassess BP control.

The REDCap forms that the pharmacists will use to record data are shown in Appendix 10

4.5 6-Month Visit Procedures

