Our working hypothesis is that there will be a greater number of medication changes in the intervention group compared to the control group. We will count the number of medication changes (dose increased, dose decreased, drug stopped, drug started) during the 12 months following the start of the intervention. The total number of medication changes will be the primary outcome measure for Aim 2. In addition, we will determine the number of pharmacist recommendations that were accepted by physicians. These are process measures: we found in our previous studies that BP improvement was primarily related to medication changes. We are assuming that changes are a sign of close monitoring. Indeed, we have used this measure previously. However, we realize that not all medication changes are equal, and thus we will record both medication trends and final treatment for each patient.

Aim 3: Determine the cost effectiveness of the intervention.

Our working hypothesis is that our intervention will be cost effective when compared to the control group. In addition, we will compare these results to previous pharmacist interventions. Because much pharmacist time is spent on non-direct patient care activities, we are convinced that our bi-directional texting approach will be both labor and cost saving. We will compute the incremental cost effectiveness ratio (ICER) using the total costs of doctor visits, pharmacist time, medications and medication changes during the 12 months of the trial. The ICER will be the difference between the control and intervention groups in average total cost

divided by the difference in average decrease of SBP and DBP. The ICER will be expressed in the dollars per mmHg reduction in BP and will be the primary outcome in this Aim.

6. Statistical Design and Power

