One interim analysis is planned after outcome data are received and the results are reported to the Data Safety and Monitoring Board from the first half of the study. The interim monitoring method of Lan and DeMets will be used with O'Brien-Fleming alpha spending function for the interim analyses. Accordingly, type I error rate of 0.00305 for the interim analysis and 0.4695 will be used for the final analyses. The current sample size of 420 patients total accommodates the interim analyses.

Aim 2 Analysis: The analysis will be done on an intent-to-treat basis regardless of the number of reported BPs or the number of pharmacist interactions with the subject. Our primary outcome will be the number of medication changes over 12 months in the control and intervention groups. We will use a GLMM based on the Poisson distribution with a log link function, and as in Aim 1 we will incorporate random effects for clinic and physician nested within clinic to account for practice heterogeneity between clinics and providers. As the observed treatment effects in those clusters are likely to be non-independent, we will include both random intercepts and random treatment effect for the intervention factor. Specifically, the model will be given as

$$\begin{aligned} \log(\mathbb{E}(Y_{cp})) &= \tau + \alpha_c + \gamma_{cp} + (\omega + \nu_c + \xi_{cp})X_{cp}, \\ (\alpha_c, \gamma_{cp})' &\stackrel{\text{iid}}{\sim} N(0, G_1), \\ (\nu_c, \xi_{cp})' &\stackrel{\text{iid}}{\sim} N(0, G_2), \end{aligned}$$

where Y_{cpi} is the number of medication changes for the i^{th} subject under the p^{th} provider within clinic c . The random effects incorporated into the final model will be chosen via AICc.

Power: Based on existing work, we expect an average of 4.9 medication changes in the intervention group (SD = 5.1) and an average of 1.1 medication changes in the control group (SD = 1.6). We would expect a difference of 3.8 changes per year with a pooled standard deviation of 3.8. In order to have 85% power to detect a difference of 3.8 or more changes with a Type I error rate of 5% and a standard deviation of 3.8, we would need 19 subjects per arm or 38 total. Considering both 14% loss to follow-up and adjusting the type I error rate for interim analysis, power of the study with our sample size of 420 will be more than adequate.

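### Aim 2: the Poisson mixed model has no term for extra spread between patients of the same physician, although the plan's own SDs point to it; the interval is likely to be somewhat too narrow (minor)

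*Combined protocol and SAP*

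**What the plan says.** Section 5 lists the number of medication changes among the secondary outcomes and makes it the main measure for Aim 2. It adds: "These are process measures".

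Section 6 (Aim 2 Analysis) states: "We will use a GLMM based on the Poisson distribution with a log link function". The random effects are for clinic and for physician nested within clinic, and "we will include both random intercepts and random treatment effect for the intervention factor". Their final form is left open: "The random effects incorporated into the final model will be chosen via AICc". Each subject contributes one count, and the model equation has no subject-level term.

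The Aim 2 power paragraph gives the expected distribution. On the treated side it reads: "we expect an average of 4.9 medication changes in the intervention group (SD = 5.1"). The comparison figure, from the same sentence, is "an average of 1.1 medication changes in the control group (SD = 1.6"). The protocol and SAP nowhere mention a dispersion parameter, a negative binomial or quasi-Poisson model, a patient-level random effect or a robust variance for this outcome.

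Section 4.4.2 describes contact that depends on the patient's own blood pressure: "The pharmacists will typically contact with the participants every 2 weeks while BP is not controlled". Once it is controlled, pharmacists "make contact at least every 2 months to support adherence and reassess BP control".

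**The concern.** Given the clinic and physician effects, a Poisson model fixes the variance of a patient's count at its mean. The plan's own SDs are well above that. Clinic and physician effects can carry some of the excess, but spread between patients of the same physician has nowhere to go except by chance into the random slopes. The standard error of the log rate ratio is then too small, and the published interval for a named secondary outcome looks more precise than it is. Part of the excess is plausibly patient-level, because contact frequency follows each patient's own control.

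**Working it through.** **Inputs.** Means and SDs: Section 6, Aim 2 power. Evaluable patients, 180 per arm: Section 6, Aim 1 power. Clinics, 3-4: Section 4.1. Number of physicians and split of the spread: not given, so assumed below.

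**1. The plan's own figure.** Pooled SD = sqrt((5.1² + 1.6²)/2) = sqrt(14.285) = 3.78, stated as 3.8. The standardised difference is 3.8/3.8 = 1. A two-sided two-sample t-test at 5% and 85% power needs 18.97, so 19 per arm (power 0.851). The stated 19 is reproduced. It uses the SDs directly and does not rest on the Poisson variance.

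**2. Dispersion.** Variance/mean = 26.01/4.9 = 5.31 (intervention) and 2.56/1.1 = 2.33 (control). A Poisson count has 1.

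**3. Upper bound on the error in the standard error (log rate ratio, 180 per arm).**
- Poisson: sqrt(1/(180×4.9) + 1/(180×1.1)) = 0.079.
- With the plan's SDs: sqrt((5.1/4.9)²/180 + (1.6/1.1)²/180) = 0.133.
- Ratio 1.70 if all the excess is within physician and nothing absorbs it; 1.39 if half is; 1.21 if a quarter is.

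**4. What the planned random effects absorb (simulation).** Assumptions: 4 clinics of 90, 1:1 allocation within clinic, all excess between patients, four independent random effects (clinic and physician, intercept and slope), AICc over all 16 subsets, Wald intervals, 918 replicates (Monte Carlo error at most 1.4 points). Target: ln(4.9/1.1) = 1.494. Gamma-shaped excess:

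| Physicians | 12 | 32 | 60 |
|---|---|---|---|
| Median model SE | 0.102 | 0.108 | 0.112 |
| True SD of estimate | 0.140 | 0.133 | 0.144 |
| Ratio, true SD / model SE | 1.37 | 1.23 | 1.29 |
| Shift of the estimate | -0.02 | -0.05 | -0.10 |
| Coverage | 83% | 87% | 80% |
| Coverage, width alone (estimates centred) | 83% | 89% | 87% |
| Two-sided null rejection (both arms 1.1, SD 1.6) | 13% | 10% | 16% |

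Over gamma, lognormal and zero-inflated excess, width-alone coverage was 83-89%. A separate calculation with Gauss-Hermite integration, no clinic level and 10-40 physicians gave true SD/model SE ratios of about 1.15-1.35.

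**5. Half the intervention-arm excess between physicians (952 replicates).** Coverage was 89-91% with AICc and 90-93% with every random effect kept. Two-sided null rejection was 7-12% and 6-10%.

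**6. Direction of the null rejections.** Two simplified simulations (physician intercept and slope both kept, no clinic level, no AICc, all excess between patients; 500 and 300 runs per cell) split the rejections by side. Nominal is 2.5% each.

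| Physicians | 12 | 30 | 60 |
|---|---|---|---|
| Favouring the intervention | 3.8%, 4.7% | 2.0%, 2.3% | 0.6%, 0.3% |
| Against the intervention | 7.4%, 6.7% | 11.0%, 10.0% | 19.4%, 19.3% |

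The asymmetry arises because a spurious slope variance s² lowers the conditional coefficient: the marginal log ratio is about coefficient + s²/2. Adding s²/2 back at 60 physicians moved the mean error from -0.108 to +0.031 and non-coverage from 21% to 11%.

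**7. At the expected effect.** 1.494/0.133 = 11.2, against 1.494/0.079 = 19.0 under Poisson.

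**The case against.** The strongest reply is that the quoted SDs are marginal. They come from other work and include spread between clinics and physicians, which the model does represent. That stands, and it is why no single size can be given. It does not rescue the model altogether. For clinic and physician effects to carry all the excess, their log-scale variance would have to be ln(1 + (26.01-4.9)/4.9²) = 0.63 and ln(1 + (2.56-1.1)/1.1²) = 0.79. Mean rates would then differ exp(2×1.96×sqrt(0.63)) = about 22-fold and, likewise with 0.79, about 33-fold between providers at the 2.5th and 97.5th percentiles. That is hard to believe.

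Section 4.4.2 also supports less than it first appears to. Contacts are not medication changes. The physician may accept, modify or decline a recommendation (Appendix 10), and the passage says nothing about the control arm. It makes patient-level spread plausible but does not measure it.

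Three stronger readings are tempting, and the documents do not support them:
- *The standard error is 1.70 times too small.* This needs all the excess within physician and no absorption by the planned random slopes.
- *Coverage falls to 76-80%.* These values occur in the simulations only at 60 physicians, and they mix the shift between conditional and marginal coefficient with the width of the interval.
- *The trial would too often claim more changes with the intervention.* From about 30 physicians such false claims are at or below nominal. With about 12 they are roughly 4-5% against 2.5%. This split was obtained without AICc selection or a clinic level.

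**Conclusion.** The point holds as a minor one. The planned Poisson model cannot represent extra spread between patients of the same physician, and the plan's own figures make some such spread likely.

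If all the excess is patient-level, the true SD of the estimate is roughly 15 to 35% larger than the model's standard error, and width-alone coverage is about 83-89%. With half the intervention-arm excess between physicians, coverage is about 89-93%. With many physicians the conditional coefficient is also pulled below the marginal ratio, so the surplus of null rejections lies mainly against the trial's hypothesis.

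These sizes rest on assumed physician numbers (12 to 60), an assumed split and assumed shapes of the excess. Nothing changes for the expected Aim 2 conclusion, the 19 per arm or the primary SBP analysis.

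**What to change.** In Section 6 (Aim 2 Analysis), replace the Poisson sentence with:

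> The marginal log rate ratio of medication changes will be estimated with a log-link model with physician-clustered robust standard errors and a t reference with (number of physicians - 1) degrees of freedom. As a supporting analysis, a negative binomial GLMM with the same clinic and physician random effects will be fitted, with the dispersion parameter always estimated and not subject to AICc selection.

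The order is deliberate. The robust interval covered 92-96% in every setting of steps 4 and 5. The negative binomial model with AICc covered 91-95% with gamma or lognormal excess, but 99-100% (too wide) with zero-inflated excess and 90-93% where physicians truly differ in treatment effect. In a harder test (32 physicians, a physician's effects in the two arms correlated 0.5), null rejection was 6-8% for the robust analysis, 9-13% for the negative binomial and 10-14% for the Poisson model.

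The cost is two sentences, a marginal rather than conditional rate ratio, and a wider interval. Setting 0.133 against the Poisson model SEs in step 4 gives 0.133/0.112 = 1.19 to 0.133/0.102 = 1.30 times the width, before the t multiplier, which adds most when physicians are few. Power stays ample, with an expected z of about 11. The number of physicians should be reported with the result, because the robust method relies on it.

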Study Title: A Pharmacist Intervention for Monitoring and Treating Hypertension Using Bidirectional Texting

Version Number/Amendment	Approval Date
Original Protocol, Version 1.0	8/3/2019
Revised Protocol, Version 2.0	11/27/2019
Revised Protocol, Version 3.0	12/30/2019
Revised Protocol, Version 4.0	7/17/2020
Revised Protocol, Version 5.0	9/21/2020

Protocol Synopsis

Protocol Title	A Pharmacist Intervention for Monitoring and Treating Hypertension Using Bidirectional Texting
Main Criteria for Inclusion	Clinic measured blood pressure of ≥ 145 mmHg or ≥ 95 mmHg at two previous clinic visits or one previous clinic visit and on the day of enrollment. Previous clinic visit BPs must be within the past 18 months and measured at least 2 weeks apart from each other.
Study Objective	To evaluate whether our scalable SMS approach combined with a pharmacist-based intervention improves BP management and that is cost effective.
Study Design	A single-site, two-arm, single-blind randomized trial
Number of Sites	1 site, 3-4 clinic locations
Study Arms	2 Study Arms a) Intervention Group- Text 7 morning and 7 evening BP values at baseline. Monitored by a study pharmacist for 12 months. Research visits at 6 and 12 months b) Control Group- Text 7 morning and 7 evening BP values at baseline. Research visits at 6 and 12 months
Total Number of Subjects	420
Duration of Study Participation	12 months
Primary Outcomes	Mean difference in systolic blood pressure between the control and intervention groups at 12 months.
Secondary Outcomes	Mean difference in diastolic blood pressure between the control and intervention groups at 12 months. Total number of medication changes (i.e., dose, discontinuation, initiation, etc.) from baseline to 12 months.

	Total cost of medications, time spent by research staff, and clinic visits per patient from baseline to 12 months.

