Additionally, the research team will conduct a 12-Month Medical Record Review for each participant. This chart review will occur separately from the 12-Month visit and will not require any effort on the part of the participant. A member of the research team will screen the participant's medical record for all clinic/quick care visits (documenting reason), any emergency room visits (documenting reason), and any hospitalizations (documenting reason and length of stay). These data will be recorded on the REDCap forms in Appendix 13. Again, multiple entries will be allowed by REDCap.

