Aim 3 Analysis: The analysis will be performed on an intent-to-treat basis regardless of the number of reported BP measurements or the number of pharmacist interactions with the subject. The perspective of this cost analysis is society in general. For each patient encounter, pharmacists will record the number of minutes spent in the following activities: medical record review, consultation, patient assessment, ordering medications, medical education, lifestyle education, BP measurement education, making recommendations, and documentation in the medical record. Pharmacist costs will be estimated by multiplying the time spent by their compensation rate. Costs for clinic visits will be obtained from the university. Utilization measures will be converted to costs per subject using the Medicare fee schedule for visits. Pharmacist and physician salaries will be obtained from the Bureau of Labor Statistics. The average wholesale drug cost for prescription medications will be obtained from Lexicomp Online (<https://online.lexi.com>). Generic prices will be used when available. The drug cost per prescription for each subject will be calculated by multiplying the average wholesale price (AWP) by frequency and dose.

We assume that subjects in the intervention and control groups will have similar characteristics. However, if there are significant differences between the subjects in these groups, costs will be predicted using a multivariate generalized linear model with a gamma family and a log link to control for these differences.

We will determine the cost of the intervention by subtracting the average total cost (pharmacist, clinic, and drugs) for the intervention group from the average total costs for the control group. The ICER is calculated as the cost differential from the intervention divided by the outcome differential from the intervention. Our primary outcome will be average decrease in SBP, and the outcome differential will be the average decrease in SBP for the control group minus the average decrease in SBP for the intervention group. The result of this analysis will be an ICER, which gives the additional cost of the intervention per mm Hg of SBP decrease.

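### Aim 3 declares a societal perspective, but the total cost in the ICER is a partial health-care cost (pharmacist, clinic and drugs), so it cannot support a societal conclusion

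*Combined protocol and SAP*

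**What the plan says.** The perspective is declared in Section 6, Aim 3 Analysis: "The perspective of this cost analysis is society in general". The cost components are then listed in three places, in three different ways:

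- Section 6, Aim 3 Analysis, builds the cost differential from "the average total cost (pharmacist, clinic, and drugs) for the intervention group" and the corresponding control total.
- Section 5, Aim 3, computes the ICER "using the total costs of doctor visits, pharmacist time, medications and medication changes during the 12 months of the trial".
- The Synopsis, under secondary outcomes, gives "Total cost of medications, time spent by research staff, and clinic visits per patient from baseline to 12 months". It names research staff time where the other two name the pharmacist.

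Section 6 also says that utilization measures will be turned into per-subject costs with a Medicare fee schedule for visits. It does not define the term. The sentence before it already gives the university as the source of clinic visit costs.

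The trial records more than these lists use. The 12-month medical record review (Section 4.6) captures "any emergency room visits (documenting reason), and any hospitalizations (documenting reason and length of stay", and Appendix 13 has a field for days in hospital. Participants are asked at the 12-month visit about ER visits and admissions outside the university system (Section 4.6, Appendix 12). Appendix 5 records the distance from home to clinic. The two sensitivity analyses described in Section 6 vary only drug prices and the way pharmacist time is valued.

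**The concern.** A societal perspective promises that costs are counted whoever bears them. A total made of pharmacist, clinic and drug costs covers only part of health-care spending and nothing borne by the participant. If the analysis is run as written, a narrow ICER will be reported under a broad label.

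Cost effectiveness is part of the study objective (Section 2.1), and the ICER is the primary outcome of Aim 3 (Section 5). The plan also expects many more medication changes with the intervention (4.9 versus 1.1 in Section 6, Aim 2). Closer monitoring and more drug changes could reduce acute-care use, through avoided events, or increase it, through harms of intensification. The monthly texting after baseline is used only by the intervention arm (Section 4.4.2, Appendix 2), so its running cost is part of the incremental cost of the intervention. Neither described sensitivity analysis would show the effect of leaving these items out.

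**Working it through.** The documents give no ICER, cost total, unit cost or event rate, so there is no planned figure to reproduce. The main check sets each component against the stated totals and the data collected.

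| Component | In a stated total? | Recorded? |
|---|---|---|
| Pharmacist time | Yes, Sections 5 and 6; the Synopsis says research staff time | Yes, minutes per encounter |
| Clinic or doctor visits | Yes, all three lists | Yes, chart review |
| Drugs | Yes, all three lists | Yes, medication forms |
| ER visits | Not named; possibly meant by utilization measures | Yes, chart review and participant report |
| Inpatient stays | Not named; no inpatient price source given | Yes; days from chart review, but no length-of-stay field in Appendix 12 for outside stays |
| Participant travel | No | Home-to-clinic distance, Appendix 5 |
| Participant time, lost productivity | No | No dedicated field on the forms shown |
| Texting platform and its set-up | No, unless the Synopsis wording on staff time covers the set-up labour | Not recorded as a cost |

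The first three rows are the whole of the stated total. Even if ER visits are added on the generous reading, no row that carries a participant-borne cost is in any list. The total is therefore not societal on any reading.

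An illustration of scale uses these inputs:

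- Arm size: 420 / 2 = 210 (Synopsis; Section 6).
- SBP difference: 17.3 − 11.6 = 5.7 mmHg (Section 6, Power). SBP is the denominator that Section 6 uses for the ICER.
- Cost per admission: $5,000 to $15,000. This is an assumption; the documents give none.

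Shift in mean cost = (net extra admissions × cost per admission) / arm size. For one net extra admission:

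- 5,000 / 210 = $23.8, about $24 per participant.
- 15,000 / 210 = $71.4, about $71 per participant.

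Shift in ICER = shift in mean cost / SBP difference:

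- 23.8 / 5.7 = $4.2 per mmHg.
- 71.4 / 5.7 = $12.5 per mmHg.

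More generally, each $100 per-participant difference between arms in omitted cost moves the ICER by 100 / 5.7 = $17.5 per mmHg, upward or downward according to which arm has the higher omitted cost.

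**The case against.** The best defence rests on the utilization sentence in Section 6. Clinic visits already have a price source, so a second sentence that prices utilization can be read as covering the other events the trial records, and the parenthesis naming three components may be shorthand. A reader might infer from the lists that ER visits are definitely excluded from the total; the documents do not establish that. This part of the defence stands. It is weaker for inpatient stays, because a fee schedule for visits does not price hospital days and no other source is named. It does nothing for travel, participant time or the platform.

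Secondly, Section 6 describes the ICER modestly, as the added cost of the intervention per mmHg of SBP decrease, and lists its components openly. A reader might conclude that the ICER fails to measure what it claims. That goes too far: the ratio is usable for what it counts, and the conflict is with the one sentence that declares the perspective.

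Thirdly, the acute-care data are less complete than they look. Length of stay comes from the record review. The outside-event form has diagnosis or reason and date only, and depends on the participant attending the 12-month visit. Adding acute care, platform and travel would still leave out participant time and productivity, so extending the list cannot by itself justify the societal label. Both observations are correct, and they shape the remedy.

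**Conclusion.** The point holds as an inconsistency between the declared perspective and the costs counted. Inpatient stays, participant travel and time, and the platform enter no stated total; the position of ER visits is unclear. As written, Aim 3 would yield a partial health-care cost per mmHg, which cannot support a societal conclusion.

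A reader might go further and infer that the ICER is biased. The documents do not show this. They give no difference between arms in acute-care use, no unit costs and no threshold for judging a shift. The figures of about $4 to $13 per mmHg rest on an assumed admission cost, an assumed net difference of one admission, all 210 participants per arm being costed, and the planned 5.7 mmHg difference. They indicate scale and do not demonstrate materiality.

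The primary SBP comparison is unaffected. The correction should still be made, because it is cheap and changes what Aim 3 can conclude.

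**What to change.** 1. In Section 6, Aim 3 Analysis, restate the perspective to match the costs counted: health-care sector, limited to pharmacist, outpatient visit and drug costs.
2. Make the component lists in the Synopsis, Section 5 and Section 6 agree, including whether the staff cost means pharmacist time or research staff time.
3. Define utilization measures and say whether ER visits are among them.
4. Report ER visits and hospital days by arm beside the ICER.
5. Add a sensitivity analysis that includes ER and inpatient costs and the platform cost. Name the inpatient price source, and state a length-of-stay assumption for stays outside the university system, since Appendix 12 records none.

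These choices should be fixed before costs by arm are seen, so that components are not selected on results.

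The cost is some rewording, one descriptive table and one further analysis, mostly on data already collected. The downsides are a narrower claim and a wide interval for the sensitivity ICER, because inpatient costs are skewed.
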